## **5. Data Collection**

Preoperative, intraoperative, and postoperative data will be collected prospectively. Mortality data will be assessed at 30 and 60 days using hospital records and telephone follow-up.

## **6. Statistical Analysis Plan**

Statistical analyses will be performed using SPSS version 22.0. Continuous variables will be presented as mean  $\pm$  standard deviation or median (interquartile range). Categorical variables will be presented as frequencies and percentages. Receiver operating characteristic (ROC) curve analysis will be used to assess the predictive performance of each scoring system. Sensitivity, specificity, and area under the curve (AUC) values will be calculated. A p-value  $< 0.05$  will be considered statistically significant.

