## **1. Study Rationale and Objectives**

This prospective observational study aims to evaluate and compare the predictive accuracy of perioperative risk scoring systems in patients undergoing gastrointestinal malignancy surgery. The primary objective is to assess the sensitivity of ASA, SAS, Portsmouth-POSSUM, ACS-NSQIP, and ARISCAT scores in predicting postoperative mortality. Secondary objectives include evaluating the ability of these scores to predict postoperative pulmonary and extrapulmonary complications, ICU admission, and length of hospital and ICU stay.

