## **2. Study Design**

This is a single-center, prospective observational study conducted at a tertiary referral hospital. No additional interventions beyond routine clinical care will be performed.

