## **3. Study Population**

Adult patients aged 18 years or older undergoing elective gastrointestinal malignancy surgery under general anesthesia who provide written informed consent will be included.

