## **4. Outcome Measures**

Primary outcome: postoperative mortality (30-day and 60-day). Secondary outcomes: postoperative pulmonary and extrapulmonary complications, ICU admission, length of hospital stay, and ICU stay.

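### The overall aim is to compare five scores, but the SAP analyses each score on its own and plans no between-score difference or interval (cheap improvement)

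*Combined protocol and SAP*

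**What the plan says.** All references are to the combined protocol and SAP.

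- **Section 1, overall aim.** The study "aims to evaluate and compare the predictive accuracy of perioperative risk scoring systems". This is the only comparative wording.
- **Section 1, objectives.** "The primary objective is to assess the sensitivity of ASA, SAS, Portsmouth-POSSUM, ACS-NSQIP, and ARISCAT scores in predicting postoperative mortality". For the rest, "Secondary objectives include evaluating the ability of these scores to predict postoperative pulmonary and extrapulmonary complications", with ICU admission and lengths of stay added. Neither sentence asks for a contrast between scores.
- **Sections 2 and 3, design and population.** "This is a single-center, prospective observational study conducted at a tertiary referral hospital", with one set of entry criteria. This implies, without saying so, that all five scores are taken on the same patients.
- **Section 4, primary outcome.** Mortality at two time points, 30 and 60 days.
- **Section 6, analysis.** "Receiver operating characteristic (ROC) curve analysis will be used to assess the predictive performance of each scoring system". Then: "Sensitivity, specificity, and area under the curve (AUC) values will be calculated". A 0.05 significance threshold follows, attached to no named test or hypothesis.

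Section 6 names no difference between scores, paired method, reference score, interval for a difference or multiplicity rule. Sections 2 to 5 add none.

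**The concern.** The study sets out to compare, but the analysis section stops at five separate ROC analyses. A reader of the results would then have five AUCs and five sets of sensitivities and specificities to lay side by side, perhaps with a p-value for each score. A per-score p-value, for instance for AUC against 0.5, shows only that a score predicts better than chance. It does not show that two scores differ. A ranking of point estimates always produces a top score, even when all five are equally good.

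At stake is the comparative conclusion alone. Without an interval for the difference, the report could not say whether an apparent lead is more than sampling noise. With no contrast fixed in advance, the choice of measure, time point and pair could also be made after the data are seen.

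**Working it through.** **1. Does any section supply a contrast?** Set side by side, the aim (section 1) asks for a comparison, the objectives (section 1) ask for description, and section 6 supplies description score by score. The objectives and section 6 agree; the aim and section 6 do not. This is the finding, and it needs no arithmetic.

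**2. Is there a figure in the plan to reproduce?** No. The documents give no sample size, expected deaths, mortality rate, effect size or power. Everything from step 4 on is illustration on assumed inputs.

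**3. How many contrasts would a comparison involve?**
- Pairs of five scores: 5 × 4 / 2 = 10.
- Mortality contrasts: 10 pairs × 3 measures (AUC, sensitivity, specificity) × 2 time points = 60.
- If 10 contrasts were each tested at 0.05 without adjustment, the chance of at least one false positive would be 1 − 0.95^10 = 0.40 under independence. The contrasts share patients and scores, so the true value would be lower.

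**4. How large a gap appears when all five scores are equally good?** Assumptions: continuous binormal scores, true AUC 0.75 for all, correlation 0.5 between scores, 5% mortality. For sensitivity, the cut-off gives 80% specificity. Simulated medians:

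| Deaths | Best-minus-worst AUC | Best-minus-worst sensitivity |
|---|---|---|
| 10 | 0.13 | 30 points |
| 30 | 0.07 | 17 points |
| 100 | 0.04 | 9 points |

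With correlation varied from 0.3 to 0.7 and true AUC from 0.70 to 0.80, the AUC gap ranges over 0.09–0.16, 0.05–0.09 and 0.03–0.05 respectively.

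**5. Hand check of the AUC column.** Under the same kind of assumptions, the median 95% half-width of a paired AUC difference (DeLong) is 0.15 with 10 deaths and 0.09 with 30. Scaling the latter by √(30/100) gives about 0.049 with 100. For five equally correlated, equally precise estimates, the median range is about 2.26 × SE(difference) / √2, where 2.26 is the median range of five independent standard normals.
- 10 deaths: 0.15 / 1.96 = 0.077; 2.26 × 0.077 / 1.414 = 0.12.
- 30 deaths: 0.09 / 1.96 = 0.046; 2.26 × 0.046 / 1.414 = 0.07.
- 100 deaths: 0.049 / 1.96 = 0.025; 2.26 × 0.025 / 1.414 = 0.04.

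These agree with the simulation to within about 0.01. With 10 and with 30 deaths, the typical gap among equal scores (0.13, 0.07) is smaller than the half-width of one paired interval (0.15, 0.09). An interval would therefore usually show that such a lead is compatible with no difference; a bare ranking would not.

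**6. What can a paired contrast detect?** Suppose one score has AUC 0.80 and the other four 0.75, with correlation 0.5. The better score has the highest observed AUC in about 46%, 67% and 94% of studies with 10, 30 and 100 deaths; chance alone would give 20%. At the first Holm step (0.05 / 10 = 0.005), any of the 10 DeLong contrasts rejects in only about 14–17% of studies with 10 to 30 deaths and about 48% with 100. These shares include false rejections among the equal scores.

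**The case against.** **The comparative wording is thin.** It appears once, in the aim sentence. A descriptive display of five AUCs from one cohort is a permissible reading of that aim, and section 6 does deliver what the primary objective asks. This stands. It limits the point to the missing uncertainty for a difference. A reader might infer that the primary objective has no analysis; the documents do not support that.

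**The harm is conditional.** A reader might also infer that the study will name a wrong best score, or that the 0.05 threshold will be used for per-score tests. No section says that a best score will be named, and the threshold is tied to nothing, so both are possibilities and not the stated plan.

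**The size is wholly assumed.** With no event count, the gap among equal scores could be 0.13 or 0.04. Scores with few levels, which would produce ties, were not modelled. This stands too, but the omission does not depend on the figures.

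**The remedy will not find the winner.** With few deaths, a tested paired contrast would usually leave a truly better score unnamed (step 6 of the working). This is correct. What the remedy adds is an honest statement of uncertainty, which a ranking lacks.

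**Conclusion.** The point holds, as a cheap improvement. The overall aim is comparative, and the statistical section contains no between-score difference and no uncertainty for one. Followed as written, the plan could answer that aim only by informal ranking. On the assumed inputs, a median AUC gap of about 0.13, 0.07 or 0.04 with 10, 30 or 100 deaths would arise among five equally good scores, so the concern is sharpest with few deaths and fades with many. It also fades if true differences are large.

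Confidence is high for the omission and lower for its consequence, which depends on an unknown number of deaths and on how the results are reported. The conclusion also rests on the implied, unstated, use of all five scores in the same patients. It is no criticism of the descriptive primary analysis.

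**What to change.** Add to section 6, before analysis:

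1. **Paired estimates.** For each pair of scores, on the same patients, report the difference in AUC with a 95% confidence interval (DeLong for correlated curves). Beside it, report the paired difference in sensitivity among deaths and in specificity among survivors, each with a 95% interval for paired proportions. Use cut-offs fixed before outcome data are seen; the documents give none, so these must be written in as well.
2. **Interpretation.** State that one score will be called better only where a paired contrast supports it. State that wide intervals mean the scores could not be separated, not that they are equivalent.
3. **Only if p-values will support claims.** State the hypothesis to which the 0.05 threshold refers. Name one measure and one mortality time point as the primary family of 10 pairs, with a multiplicity rule such as Holm. Report the other 60 − 10 = 50 mortality contrasts as estimates with intervals.

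**Cost.** A few sentences and a little extra analysis of data already to be collected, possibly with software beyond the package named; no change to care or data collection. With few deaths the intervals will be wide: under the assumptions above, the half-width for a paired sensitivity difference is about 34–37 points with 10 deaths and 11 with 100. DeLong intervals also cover slightly less than stated when deaths are few (about 93% instead of 95% with 10), which the plan should note as a caution. The change guards against false winners; it does not give the study power to identify a truly better score from few deaths.
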